6.11 Efficacy outcome

The efficacy outcome will be symptomatic recurrence of venous thrombosis or asymptomatic deterioration.

Symptomatic recurrence of venous thrombosis or asymptomatic deterioration should be documented using the appropriate imaging test.

6.12 PK/PD assessments - amended

Blood samples will be taken for PK and PD measurements.⁴⁴ The number and volume of PK/PD blood samples represents the minimum amount of blood needed for adequate analysis (sparse sampling approach). The following blood samples will be taken:

- 1) PK/PD samples at visit 2,
- 2) PK/PD sample at visit 3, and
- 3) PK/PD sample at visit 4.

⁴² Comparator arm was removed via Amendment 4 (see Section 16.2.2.30)

⁴³ Section modified via Amendment 4 (see Section 16.2.2.31)

⁴⁴ Section modified via Amendment 4 (see Section 16.2.2.32)

The exact time of rivaroxaban dosing and PK/PD blood sampling will be documented in the eCRF. If, for any reason, PK/PD samples are taken outside of the pre-specified time window, the exact time that the sample was taken should be recorded and not the time of the time window.

If rivaroxaban was temporarily stopped at the time of a study visit (e.g. if treatment was temporarily stopped prior to visit 3), sampling of blood for PK/PD analysis according to this visit's schedule should be postponed until rivaroxaban treatment has been restarted and sustained for at least 3 days.

If a blood sample is taken from a central line, 3 mL of blood should be discarded.⁽¹⁶⁾ In children from 6 months to 1 year old, it might not be possible to withdraw blood from central venous line due to the amount of blood required especially at visit 2. In this case, it is advised to withdraw blood from a peripheral catheter. If a blood sample is taken from a peripheral catheter, fluid is to be withdrawn from the line until all is removed and blood is sampled. An anesthetic cream can be applied to minimize pain from drawing of blood from a vein. Central venous lines and peripheral catheters that are used in this study should only be flushed with saline.

The prothrombin time, activated partial thromboplastin time and anti-factor Xa activity (anti-Xa) will be used to assess the pharmacodynamic effects after administration of the study drug.

Detailed information about the handling and labeling of the samples will be provided in the laboratory manual.

The data obtained from the blood samples taken will be pooled and analyzed using population approaches to estimate the PK/PD profile of rivaroxaban. Details for the population PK/PD analysis will be described in a separate evaluation plan.

6.13 Study booklet - amended

Parents/children will receive a booklet with the following information:

- The local medical contact person and emergency telephone number
- The visit schedule provided by the IxRS, including dates of telephone and/or hospital visits
- Instructions to keep empty medication packages and unused study medication.
- How to take rivaroxaban
- Calendar to track the date and time of food and study drug intake as well as the volume of fluid taken.⁴⁵

6.14 Study committees

6.14.1 Steering committee

The steering committee has the overall scientific responsibility of the study. Its tasks and responsibilities are:

⁴⁵ Comparator arm was removed via Amendment 4 (see Section 16.2.2.33)

- To facilitate and approve the final protocol
- To help select the investigators network
- To support and organize the national logistics in the initiation and conduct of the study
- To ensure a scientifically sound and safe conduct of the study
- To decide on the DMC recommendations
- To guarantee the integrity of data collection and analyses
- To monitor progress of study enrollment
- To assist in the analysis and presentation of the results
- To decide on the publication and presentation policy of final results and ancillary studies.

6.14.2 Central independent adjudication committee (CIAC)

All index venous thrombotic events, and all suspected recurrent venous thromboembolic events, asymptomatic deterioration in the thrombotic burden on repeat imaging, bleeding, other vascular events and deaths that occur after visit 2 including the 30 day post treatment period, will be evaluated by a CIAC, which will be provided with all relevant documentation related to the events. The procedures followed by the CIAC will be described in an adjudication manual. Adjudication results will be the basis for the final analyses.

6.14.3 Data monitoring committee (DMC)

This committee has the responsibility to provide the steering committee with recommendations related to the protection of the children's safety, including stopping recruitment and study treatment. For that purpose, the DMC will regularly review all incidences of serious adverse events (SAEs), recurrent venous thromboembolic events and bleeding. Organizational aspects, responsibilities, and processes will be described in the DMC charter.

7. Statistical and analytical methods

7.1 General considerations

The plan described in the following sections will be detailed in a Statistical Analysis Plan (SAP). The SAP will accommodate protocol amendments or unexpected issues in study execution or data that affect planned analyses. Any revision will be clearly identified in the final SAP, issued prior to data base lock. If not stated otherwise, the following statistical specifications will apply.

7.2 Analysis sets - amended

Full analysis set (FAS): This analysis set will include all enrolled children.

Safety analysis set (SAS): This analysis set will include all enrolled children who received at least one dose of study medication.

Per protocol set (PPS): This population includes all enrolled children who completed the 30-day treatment period. The PPS may also exclude major protocol deviations. Further details will be specified in the Statistical Analysis Plan.

Listing only set (LOS): This population includes all screening failures.⁴⁶

7.3 Demographic and other baseline characteristics - amended

Summary statistics (arithmetic mean, standard deviation, median, minimum and maximum for quantitative variables) will be presented by age group. Frequency tables for qualitative data will be provided. Medical history findings will be summarized using Medical Dictionary for Regulatory Activities (MedDRA) terms.⁴⁷

7.4 Safety analysis - amended

All safety analyses will be performed on the SAS population. The analysis will primarily focus on bleeding that occurred during or within 2 days after stop of study treatment. Bleeding events observed later will be described separately.

Individual listings of major and clinically relevant non-major bleeding will be provided. The incidence of bleeding will be summarized descriptively. If a sufficient number of bleeding events is observed, factors which potentially influence the occurrence of bleeding will be assessed by appropriate statistical procedures.

Quantitative data will be described by the summary statistics and will be presented descriptively for the original data as well as for the difference to baseline. Frequency tables will be provided for qualitative data.⁴⁸

7.5 Efficacy analysis - amended

All efficacy analyses will be performed on the FAS population. The occurrence of recurrent venous thromboembolism and asymptomatic deterioration in thrombotic burden will be summarized by age group.⁴⁹

7.6 PK/PD analysis

PK/PD modeling, using population approaches will be used to describe the pharmacokinetics of rivaroxaban, including potential influence of relevant co-variables, and to relate anticoagulant parameters of rivaroxaban with plasma concentrations. Details will be given in a separate detailed PK/PD evaluation plan.

⁴⁶ Comparator arm was removed via Amendment 4 (see Section 16.2.2.34)

⁴⁷ Section was modified via Amendment 4 (see Section 16.2.2.35)

⁴⁸ Comparator arm was removed via Amendment 4 (see Section 16.2.2.36)

⁴⁹ Section was modified via Amendment 4 (see Section 16.2.2.37)

7.7 Interim analyses

No interim analysis will be performed.

7.8 Determination of sample size - amended

A total of 20 children who took at least one dose of study medication are planned to be enrolled in the study.⁵⁰ The sample size does not originate from a formal sample size calculation, but is based on a feasibility assessment because of the very low incidence of venous thrombosis in children, and on the pharmacokinetic moderate inter-individual variability of rivaroxaban. Based on past experience in obtaining parental consent in this indication, it is estimated that fewer than 10% of eligible children can be enrolled in this study.

7.9 Adverse events (AE) - amended

Individual listings of adverse events (including age, weight, height, gender, adverse event as reported, start, duration, severity and relation to study drug) will be provided. The incidence of treatment-emergent adverse events will be summarized by age group using MedDRA preferred terms grouped by primary system organ class.⁵¹

7.9.1 Definitions

7.9.1.1 Adverse event (AE)

An AE is any untoward medical occurrence in a subject administered with a pharmaceutical product and does not necessarily have to have a causal relationship with this treatment. An AE can therefore be any unfavorable and unintended sign (including an abnormal laboratory finding), symptom, or disease temporally associated with the use of a drug, whether or not considered related to the drug. AE associated with the use of a drug, whether or not considered drug related, includes AE occurring in the course of the use of a drug, from an overdose whether accidental or intentional, from drug abuse, from drug withdrawal, or if there is a reasonable possibility that the event occurred purely as a result of participation in the study, even if it is not related to the drug.

The clinical manifestation of any failure of expected pharmacological action is not recorded as an AE, if it is already reflected as an outcome captured in the eCRF, except if the event fulfills the criteria for a “serious” AE.

A surgical procedure or intervention that was planned prior to visit 2 should not be recorded as an AE. Conditions, including abnormal physical examination findings, symptoms, and diseases will be recorded as medical history if they started before visit 2 and:

- no symptoms or treatment are present until visit 2, or
- symptoms or treatment are present after visit 2 at unchanged intensity.

If the condition started or deteriorated after administration of study drug at visit 2, it will be documented as adverse event.

⁵⁰ Total number of subjects reduced via Amendment 4 (see Section 16.2.2.38)

⁵¹ Section modified via Amendment 4 (see Section 16.2.2.39)

7.9.1.2 Serious adverse event (SAE)

An SAE is any untoward medical occurrence that at any dose is resulting in death, is life-threatening (i.e. the patient was at risk of death at the time of the event), requires hospitalization or prolongation of existing hospitalization unless the admission results in a hospital stay of less than 12 hours, is pre-planned, or is not associated with an AE (i.e. social hospitalization for purposes of respite care), results in persistent or significant disability/incapacity. In addition, SAE is a congenital anomaly or a birth defect or an important medical event, including associated invasive treatment, as judged by the investigator. For reporting of a SAE, local regulations take precedence if more stringent definitions are applicable.

7.9.1.3 Unexpected AEs

An unexpected AE is any adverse drug event whose specificity or severity is not consistent with the investigator brochure (or package inserts for marketed products). Also, reports which add significant information on specificity or severity of an already documented AE constitute unexpected AEs. For example, an event more specific or more severe than described in the investigator brochure would be considered "unexpected". Specific examples would be 1) acute renal failure as a labeled adverse event with a subsequent new report of interstitial nephritis and 2) hepatitis with a first report of fulminant hepatitis.

7.9.2 Relationship of AE to the study drug

The assessment of the causal relationship between an AE and the use of medication is a clinical decision based on all available information at the time of the completion of the eCRF and is based on whether there was a "reasonable causal relationship" to the medication.

An assessment of "no" would include the existence of a clear alternative explanation, e.g. mechanical bleeding at surgical site, or non-plausibility, e.g. the child while on a bike is struck by an automobile when there is no indication that the drug caused disorientation that may have caused the event. An assessment of "yes" indicates that there is a reasonable suspicion that the AE is associated with the use of the drug. Factors in assessing the relationship of the AE to study treatment include the temporal sequence from drug administration (the event should occur after the drug is given) and the length of time from drug exposure, recovery on drug discontinuation (de-challenge), and recurrence on drug re-introduction (re-challenge), underlying, concomitant, or intercurrent diseases should be evaluated in the context of the natural history and course of any disease the child may have, concomitant medication or treatment and, finally, the pharmacology and pharmacokinetics of study treatment.

7.9.3 Causal relationship to protocol-required procedure

The assessment of a possible causal relationship between the AE and protocol-required procedure is based on the presence of a reasonable relationship.

7.9.4 Intensity of an AE, action taken and outcome

The intensity of an AE is assessed as mild (usually transient in nature and generally not interfering with normal activities), moderate (sufficiently discomforting to interfere with normal activities), and severe (prevents normal activities).

Any action on study treatment to resolve the AE is to be documented as either: study drug withdrawn, interrupted, dose not changed, not applicable or unknown. Other specific treatment(s) of AEs will be documented as: none, remedial drug therapy or other. The outcome of the AE is to be documented as: recovered/resolved, recovering/resolving, recovered/resolved with sequelae, not recovered/not resolved, fatal or unknown.

7.9.5 Assessments and documentation of adverse events

Complications that occur during the screening period between visit 1 and visit 2 will not be reported as AEs, because no study medication or study related procedures are required during this period, but may be documented in the medical history, if applicable.

After study drug intake at visit 2, documentation of AEs must be supported by an entry in the subject's file. A laboratory test abnormality considered clinically relevant, e.g. causing the subject to withdraw from the study, requiring treatment or causing apparent clinical manifestations, or judged relevant by the investigator, should be reported as an AE. Each event should be described in detail along with start and stop dates, severity, relationship to study drug, action taken and outcome.

When assigning the cause of death, "death" should not be recorded as an AE on the AE page. Instead, "death" is the outcome of underlying AE(s).

7.9.6 Reporting of serious adverse events

All investigators will be thoroughly instructed and trained on all relevant aspects of the reporting obligations for SAEs. This information, including all relevant contact details, is summarized in the investigator site file and will be updated as needed.

SAEs occurring after study drug intake at visit 2 until 1 month after the last dose must be reported within 24 hours of the investigator's awareness. Reports should be as complete as possible, and must be followed up until resolution or stabilization. When required, and according to local law and regulations, SAEs must be reported to the ethics committee and regulatory authorities.

If reported, SAEs occurring after the protocol-defined observation period will be processed by Bayer according to all applicable regulations.

Bayer will inform all investigational sites about the occurrence of suspected unexpected serious adverse reaction/s (SUSARs) according to all applicable regulations.

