The study will be initiated with the age group between 2 and less than 6 years. Once the age- and body weight adjusted dosing regimen has been finally confirmed for the age group between 6 months and less than 2 years in phase I, and approved by the data monitoring committee and steering committee, enrollment will be extended to this age group. Before enrollment of this age group is implemented and the IxRS is activated, the investigators and their IRBs will receive a formal notification, specifying the exposure results and safety outcomes.

Study description

Children who have been treated for at least 2 months or in case of catheter-related thrombosis, treated for at least 6 weeks with LMWH, fondaparinux and/or VKA for symptomatic or asymptomatic venous thrombosis will receive age- and body weight-adjusted rivaroxaban. Before first study treatment administration, the documented index thrombotic event will be confirmed by the central adjudication committee (CIAC) for the child to be eligible for the study.

Allocation to treatment will be done centrally by an interactive voice/web response system (IxRS). The investigator will provide the IxRS with study center identification, the child's date of birth (day, month and year), gender, weight and clinical presentation.

Please refer to the IxRS manual for further details.

The IxRS will initially restrict enrollment to children in the age group between 2 and less than 6 years. Once the age- and body weight adjusted dosing regimen has been confirmed for the age group 6 months to < 2 years, the IxRS will allow enrollment for this age group as well.

Children will receive rivaroxaban for a total of 30 days.¹⁸

The treatment period will be followed by a 30-day post study treatment period, regardless of the duration of study drug administration. After cessation of study treatment, it is at the investigator's discretion to continue with anticoagulants.

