6.1 Study visits - amended

The study has 5 planned visits (see [Figure 1–1](#)).

Visit 1 is a screening visit and will be a hospital visit. This visit is to identify potential eligibility of children who are treated with anticoagulants for confirmed symptomatic or asymptomatic venous thrombosis. This visit will take place 60 to 10 days before Visit 2.

Visit 2 is the first study drug administration day and will be a hospital visit. Eligible children will receive rivaroxaban for 30 days.

Visit 3 and Visit 4 are the treatment and end of treatment visits, respectively. These visits will be hospital visits which will take place at Day 15 ± 5 days, and Day 30 ± 3 days, respectively. At visit 2, 3 and 4, PK/PD blood samples will be drawn. At Visit 4, the study medication will be stopped. After cessation of study treatment, it is at the investigator's discretion to continue with anticoagulation, as needed. Repeat imaging will be obtained if applicable.

Visit 5 is the 30 day post treatment contact visit and will be a hospital visit or a telephone contact. It will take place at Day 60 ± 7 days. This visit will be the last study visit.

In children who prematurely discontinue study medication, visit 5 will take place 30 ± 7 days after premature discontinuation.³⁴

6.2 Visit 1 - Screening visit at 60 to 10 days before Visit 2 - amended

The parents/legal guardians will be given explanation about the study and will be given sufficient time to consider participation of their child in the study. Parents/legal guardians who are willing to have their child participating in the study will be asked to sign an informed consent form.

Screening will only be performed after having received informed consent. Children who pass the screen of inclusion and exclusion criteria can be enrolled into the study.

Then demographic data, medical history, height/length, blood pressure and anticoagulant medication will be collected.

The images of the index venous thrombotic event need to be collected and the adjudication package needs to be completed and sent to the central adjudication office. The CIAC will assess the images and will inform the investigator about their decision.

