6.4 Visit 3 - Treatment visit at Day 15 (+/- 5 days) - amended

- Check for potential study outcomes. If a suspected study outcome occurred, an adjudication package needs to be compiled and sent to the adjudication office.
- Check for adverse events.
- Administer the next rivaroxaban dose and document the volume and type of fluid used to predilute the rivaroxaban oral suspension, as well as the volume and type of fluid taken after the study drug administration.
- Document the exact time of drug intake and type of meal the child took 2 hours before, during and after drug administration
- Complete the Taste-and-Texture Questionnaire for children older than 4 years
- At 2 – 8 hr after drug intake, collect a post-dose PK blood sample followed by the PD blood sample
- Document the exact time of blood sampling for PK/PD.
- Perform drug accountability and assess compliance
- Check changes in concomitant medications
- Update eCRF.
- Inform that on the day before visit 4
 - the evening dose of rivaroxaban should be taken as late as possible (i.e. closely before the child goes to bed) and medication should not be taken on the day of visit 4
 - 1) to document in the study booklet the exact time of the last dose taken on the day before Visit 4, 2) the exact time and type of meal the child took 2 hours before, during and after study drug administration, 3) the volume and type of fluid used to predilute the rivaroxaban oral suspension and 4) the volume and type of fluid taken after the study drug administration. ^{38, 39}

If a child discontinues study treatment permanently before visit 3, visit 3 will still need to take place:

- Check for potential study outcomes. If a suspected study outcome occurred, an adjudication package needs to be compiled and sent to the adjudication office
- Check for adverse events. If an adverse event occurred, update the eCRF
- Perform drug accountability and assess compliance
- Check changes in (concomitant) medications
- No blood sampling for PK/PD is required.

³⁸ Section modified via Amendment 1 (see Section 16.1.2.4)

³⁹ Section modified via Amendment 4 (see Section 16.2.2.28)

6.5 Visit 4 - End of study treatment visit at Day 30 (+/- 3 days) - amended

No study medication should be taken anymore.

- Check for potential study outcomes. If a suspected study outcome occurred, an adjudication package needs to be compiled and sent to the adjudication office
- Check for adverse events.

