6.3 Efficacy

All efficacy analyses will be performed on the full analysis set population based on the outcomes confirmed by the CIAC. Incidence proportions will be calculated for the efficacy outcomes (see Section 3.3) overall and by age stratum for the rivaroxaban group and for the standard of care group (randomized before Protocol Amendment 4) separately. The analyses described above will include events up to the end of intended study treatment (30 days after study medication assignment) regardless of the actual stop date of study medication.

In addition if there is at least one confirmed recurrent event in the corresponding time period, the analyses described above will be performed counting only events that occurred during study treatment or within 2 days after stop of study medication (i.e. treatment-emergent) on the safety population as well.

Proportion of events that occurred more than 2 days after stop of study medication up to 30 days will be described (denominator: number of subjects entering the observational period) if there is at least one confirmed recurrent event in the corresponding time period.

In addition, all descriptive efficacy analyses will be performed on the per protocol population as a supportive analysis.

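### The two-sided window on the last contact can leave the 30-day post-treatment period 7 days short of full observation, or 9 in the extreme pairing of visits

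*Protocol*

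**What the plan says.** **Period to be covered.** Protocol 3 has treatment followed by 30 days of post-treatment observation, however long the child was treated. Protocol 6.6 gives documentation of that period as the purpose of Visit 5. Protocol 6.14.2 and SAP 3.3 extend adjudication through it. Protocol 7.9.6 requires SAEs "until 1 month after the last dose must be reported". SAP 6.3 plans, for efficacy: "Proportion of events that occurred more than 2 days after stop of study medication up to 30 days will be described". The denominator is every child who enters the observational period, and the summary is produced only if at least one recurrence is confirmed in that period.

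**Contacts planned.** Protocol 6.1 fixes Day 1: "Visit 2 is the first study drug administration day". Visits 3 and 4 are at "Day 15 ± 5 days, and Day 30 ± 3 days, respectively". On Visit 5 it says: "It will take place at Day 60 ± 7 days. This visit will be the last study visit". After premature discontinuation, Visit 5 is instead 30 ± 7 days after stopping (Protocol 6.1 and 6.6). It may be a telephone call.

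**Last dose.** Protocol 6.1 ties the stop to the visit: "At Visit 4, the study medication will be stopped". Protocol 6.4 asks for a late evening dose the day before, and "medication should not be taken on the day of visit 4". Protocol 3 also says: "Children will receive rivaroxaban for a total of 30 days".

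**The concern.** The period of interest runs from the last dose, but a completer's last contact is counted from Day 1 and may come up to a week early. Two windows then add up, one on Visit 4 and one on Visit 5. No scheduled contact is required at or after day 30 following the last dose.

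Two things are at stake. First, an event between an early Visit 5 and day 30 is found only if someone volunteers it. Second, the SAP's post-treatment efficacy proportion has no person-time, no censoring at last contact and no count of children with full follow-up. A child last contacted on day 21 or 23 therefore stays in the denominator as if followed to day 30. The only dropout sensitivity analysis (SAP 6.3.1) ends at Visit 4.

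**Working it through.** **Inputs**
- Visit 4 = Day 30 + b, with b from −3 to +3: Day 27 to 33 (Protocol 6.1).
- Last dose = the evening before Visit 4 = Day 29 + b: Day 26 to 32 (Protocol 6.4).
- Visit 5, completers = Day 60 + a, with a from −7 to +7: Day 53 to 67 (Protocol 6.1).
- Visit 5, early stoppers = stop + 30 + a (Protocol 6.1 and 6.6).
- One month is taken as 30 days. Delayed first doses after VKA (Protocol 5.1.1.1) are ignored.

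**Step 1: the plan's own figure.** Nominally, 60 − 30 = 30 days from Visit 4, or 60 − 29 = 31 days from the last dose. The stated 30 days is reproduced, so on nominal days the schedule covers the period.

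**Step 2: range allowed by the windows.** For completers, gap = (60 + a) − (29 + b) = 31 + a − b.
- Minimum 31 − 7 − 3 = 21 days (Visit 4 on Day 33, Visit 5 on Day 53); maximum 31 + 7 + 3 = 41 days.
- If the last dose may not fall after Day 30, the minimum is 53 − 30 = 23 days.
- Early stoppers: 30 − 7 = 23 to 30 + 7 = 37 days.

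Unobserved days are 30 − 21 = 9 (9/30 = 30%) or 30 − 23 = 7 (7/30 = 23%). Against the SAP's window of post-treatment days 3 to 30, which is 28 days, that is 9/28 = 32% or 7/28 = 25%.

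**Step 3: how often, if visit days are uniform in their windows (assumption).**
- A completer has fewer than 30 days when a − b ≤ −2. Counting a for b = −3, …, +3 gives 3 + 4 + 5 + 6 + 7 + 8 + 9 = 42 of 7 × 15 = 105 pairs, or 40%.
- Days lost over those pairs: 6 + 10 + 15 + 21 + 28 + 36 + 45 = 161, so the mean is 161/105 = 1.5 days per completer.
- Of the 42 short pairs, 14 are short by only 1 or 2 days. Six of the 105 (6%) are short by 7 or more, and one pair gives 21 days.
- With the last dose capped at Day 30, the counts become 3 + 4 + 5 + 6 + 7 + 7 + 7 = 39 of 105 (37%), with mean loss (6 + 10 + 15 + 21 + 28 + 28 + 28)/105 = 136/105 = 1.3 days.
- Early stoppers: short when a < 0, which is 7 of 15 days (47%). A child who stops in the first few days may have the still-required Visit 4 (Protocol 6.5) after Visit 5, which lengthens observation a little; this is ignored.

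**Step 4: effect on the efficacy proportion, with a constant hazard (assumption).** Take a true 10% risk over days 3 to 30, so h = −ln(0.90)/28.
- Every child last contacted on day 21 (19 days seen): 1 − exp(−19h) = 6.9%.
- Every child last contacted on day 23 (21 days seen): 1 − exp(−21h) = 7.6%.
- Average case for 20 children: 1.53/28 = 5.5% of the window is lost, so about 20 × 0.10 × 0.055 = 0.11 events are missed.

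**Step 5: which analyses reach into the gap.** Bleeding and treatment-emergent AEs end 2 days after the last dose, at most Day 32 + 2 = Day 34. Main efficacy ends 30 days after assignment, and early stoppers are still seen at Visit 4. None of these depends on the timing of Visit 5.

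**The case against.** The strongest reply is that this is an ordinary visit tolerance in a small descriptive study. The nominal schedule gives the full period, 21 days is 1 of 105 pairs, most shortfalls are a few days, and no main analysis is touched. Anticoagulation after stopping is at the investigator's discretion, so the period is not a clean estimate for rivaroxaban anyway. All of that stands, and it sets the size of the point.

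It is also fair that SAE reporting does not hang on Visit 5. The duty follows the investigator's awareness, later SAEs are processed if reported, families hold an emergency number (Protocol 6.13) and unscheduled visits are allowed (Protocol 6.7). Protocol 7.9.6 and 6.1 therefore do not contradict each other. Passive reporting still finds less than a planned contact. For recurrence it is uncertain as well, because Protocol 7.9.7 exempts efficacy outcomes from SAE reporting while 7.9.1.1 keeps serious ones in.

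SAP 4.3 lists days to last visit for children who stop treatment early, so their short follow-up would be visible. It plans no such listing for completers.

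A reader might infer that unobserved days are counted as event-free for bleeding and SAEs too. The documents do not support that. The denominator in question belongs to the post-treatment efficacy proportion alone. SAP 6.2 only describes late bleeding separately, with no denominator specific to that period, and no post-treatment SAE proportion is planned.

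**Conclusion.** The point holds as a minor one. The visit windows do not guarantee the 30 days of observation that the protocol promises. A compliant shortfall of 7 days is possible on every reading. Nine days is possible only if dosing runs to the eve of a Day 33 visit; Protocol 3 and 6.1 leave open whether it may, and the conclusion does not depend on the answer.

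With evenly spread visits, roughly 40% of completers (37% if the last dose is capped at Day 30) and 47% of early stoppers fall short, by 1.5 days on average across all completers. The consequence is slight possible understatement of post-treatment recurrence, and incomplete active capture of late bleeding and SAEs. Because the efficacy summary appears only after a confirmed event, one missed recurrence among about 20 children could also remove it.

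It would be wrong to read this as bias in the study's principal results, or to treat 21 days as typical follow-up. The 40% and 47% rest on uniform visit days, and the effect sizes on an assumed 10% risk and constant hazard; the documents give neither.

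**What to change.** In Protocol Figure 1–1 and sections 6.1 and 6.6, count Visit 5 from the actual last dose for completers, as is already done from discontinuation for early stoppers. Make the window one-sided for all children: not before day 30 after the last dose, for example 30 to 37 days, by telephone if needed. Minimum follow-up then rises from 21 or 23 days to 30, and no days are left unobserved.

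If the windows stay, change SAP 6.3 so that the post-treatment summary censors at last contact, and report how many children were followed for the full 30 days. Extending the SAP 4.3 listing of days to last visit to completers would show the shortfall directly.

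The cost is a visit-window amendment or a short SAP edit. Some contacts move about a week later. The latest possible completer contact moves from Day 67 to Day 32 + 37 = Day 69.
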